16.52 Overall Response Rate (ORR)

Overall response rate is defined as the number of patients with a complete response (CR) or partial response (PR) (as defined by the RECIST 1.1) divided by the number of evaluable patients in each arm at 12 months post registration. ORR will be compared between the 2 treatment arms. Confidence intervals for the true success proportion will be calculated according to the approach of Clopper and Pearson.

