13.0 Treatment/Follow-up Decision at Evaluation of Patient

- 13.1 Patients who have CR, PR, or SD will continue treatment per protocol for a maximum of 24 cycles. Subsequent treatment is at the discretion of their attending physician.
- 13.2 Patients who develop PD while receiving therapy or choose an alternative therapy will go to the event-monitoring phase and be followed for survival (i.e. event-monitoring phase) every 3 months (± 7 days) for 3 years after randomization (per Section 18.0). Subsequent treatment is at the discretion of their attending physician.
- 13.3 Patients who go off protocol treatment for any reason will go to the event-monitoring phase and be followed for survival (i.e. event monitoring phase) every 3 months (± 7 days) for 3 years after randomization (per Section 18.0). Subsequent treatment is at the discretion of their attending physician.
- 13.4 A patient is deemed *ineligible* if after registration, it is determined that at the time of registration, the patient did not satisfy each and every eligibility criteria for study entry. The patient may continue treatment off-protocol at the discretion of the

physician as long as there are no safety concerns, and the patient was properly registered. The patient will go directly to the event-monitoring phase of the study (or off study, if applicable).

- If the patient received treatment, all data up until the point of confirmation of ineligibility must be submitted. Event monitoring will be required per Section 18.0 of the protocol.
- If the patient never received treatment, on-study material must be submitted. The patient will not be followed for survival.

13.5 A patient is deemed a *major violation*, if protocol requirements regarding treatment in cycle 1 of the initial therapy are severely violated that evaluability for primary end point is questionable. All data up until the point of confirmation of a major violation must be submitted. The patient will go directly to the event-monitoring phase of the study. The patient may continue treatment off-protocol at the discretion of the physician as long as there are no safety concerns, and the patient was properly registered. Event monitoring will be required per Section 18.0 of the protocol.

13.6 A patient is deemed a *cancel* if he/she is removed from the study for any reason before any study treatment is given. On-study material and the Off Treatment Form must be submitted. The patient will not be followed for survival.

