16.13 Final Analysis

Efficacy analysis will be conducted when at least 83 death events, across

both arms combined, have been observed. The stratified log-rank test will be used for decision making except when there are 0 events in any of the strata; in that case, the un-stratified log-rank will be used for decision making. If the 1-sided p-value is > 0.15 for panitumumab compared to standard therapy (TAS-102 or regorafenib), which corresponds to a hazard ratio (HR) > 0.797 , panitumumab will be considered as ineffectual; if the 1-sided p-value ≤ 0.15 (equivalently, HR ≤ 0.797), panitumumab will be considered as promising for future study. All eligible patients who sign the consent form, are randomized, and received any protocol treatment are considered evaluable for this endpoint.

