16.15 Power and Sample Size

The primary goal is to compare the OS between patients who are randomized to panitumumab and those randomized to standard therapy (TAS-102 or regorafenib). The null hypothesis is that the panitumumab arm does not show a superior OS outcome compared to standard therapy (TAS-102 or regorafenib). The alternative hypothesis is that the panitumumab arm has improvement in OS compared to standard therapy (TAS-102 or regorafenib).

We will enter 53 evaluable patients to each arm of the study using a 1:1 randomization scheme (106 evaluable patients in total); unless the study is stopped early. Stratification factors are defined in section 5.0. With 53 evaluable patients per arm, we have 80% power to detect an improvement in the median OS from 6.5 to 10 months (HR=0.65), assuming a 1-sided significance level of 0.15 and an accrual rate of 8 patients per month. The trial has a single interim analysis for futility, adopting the Rho family (Rho=1.5) beta spending function for controlling the overall type II error rate and will be considered non-binding.

16.151 Operating Characteristics

The table below shows the operating characteristics assuming the OS follows the exponential survival function along with a one-sided significance level of 0.15.

The table below includes the operating characteristics according to the monitoring plan outlined above. The proportion of times that 1) the study would stop early at the interim analysis due to futility of panitumumab, and 2) the study would conclude panitumumab is superior to TAS-102 or regorafenib at the final analysis, are tabulated by true OS median survival times and equivalent true

hazard ratios for OS by treatment groups.

True median overall survival (months) ¹		True Hazard Ratio	% of times the study will be stopped for futility at the interim analysis ²	% of times that panitumumab is deemed superior at the final analysis ²
TAS-102 or regorafenib	panitumumab			
6.5	6.5	1	47.7	14.1
6.5	7.2	0.90	34.3	26.8
6.5	7.9	0.82	24.3	41.9
6.5	8.6	0.76	16.5	56.7
6.5	9.3	0.70	11.2	69.9
6.5	10	0.65	7.5	79.4

¹ Although we use the median OS to illustrate each scenario, the hypothesis testing is based on the entire survival curve.

² Proportions are based on 50,000 replicates in a simulation study

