16.2 Sample Size

We plan to randomize at least 106 eligible patients (53 to panitumumab; 53 to standard therapy (TAS-102 or regorafenib). We anticipate randomizing an additional 14 patients to account for ineligibility, cancellation, major treatment violation, or other reasons. Therefore, maximum accrual is projected to be 120 patients.

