16.53 Clinical Benefit Rate

Clinical benefit rate is defined as the number of patients with a complete response (CR), partial response (PR), or stable disease for ≥ 6 months (as defined by the RECIST 1.1) divided by the number of evaluable patients in each arm. Confidence intervals for the true success proportion will be calculated according to the approach of Clopper and Pearson.

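### Does the undefined word evaluable leave the response-rate denominators, and even the survival analysis set, open for patients with a major violation?

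*Combined protocol and SAP*

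**What the plan says.** - **Response endpoints.** Section 16.52 divides responders by the patients evaluable: "divided by the number of evaluable patients in each arm at 12 months post registration". Section 16.53 also has "divided by the number of evaluable patients in each arm", with no time point. Neither says who is evaluable. Section 16.5 makes all secondary p-values descriptive.
- **OS.** Section 16.13 does define the set. Eligible patients who gave consent, were randomized and "received any protocol treatment are considered evaluable for this endpoint". It makes no exception for major violations.
- **Adverse events.** Section 16.54 takes eligible patients who started treatment.
- **Major violation.** Section 13.5 applies the label when "protocol requirements regarding treatment in cycle 1 of the initial therapy are severely violated that evaluability for primary end point is questionable". It adds "All data up until the point of confirmation of a major violation must be submitted", and then moves the patient to event monitoring.
- **Other early stops.** Section 13.3: "Patients who go off protocol treatment for any reason will go to the event-monitoring phase and be followed for survival".
- **Numbers.** Section 16.15 plans 53 evaluable patients per arm, 106 in total. Section 16.2 calls the 106 eligible and adds: "We anticipate randomizing an additional 14 patients to account for ineligibility, cancellation, major treatment violation, or other reasons". Maximum accrual is 120.

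**The concern.** A patient who is eligible, starts treatment and has a severe cycle 1 violation is evaluable for OS under Section 16.13. Section 13.5 calls that same evaluability questionable. Section 16.2 budgets extra patients for such violations, which seems pointless if they already count toward the 106. Two readings therefore appear possible: keep these patients, or drop them.

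For response the denominator is the sensitive part. The first restaging is at cycle 3 (Section 4.0), so a patient removed for a cycle 1 violation may have no post-baseline scan and could then enter only as a non-responder. The 12-month phrase in Section 16.52 is not explained either.

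The larger worry is OS, which alone decides whether panitumumab is called promising. Treatment is not blinded (an infusion against tablets), and the plan does not say who classifies a major violation, or when. If membership of the OS set were really open, it could be settled after outcomes were known.

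**Working it through.** **1. The design figures do not depend on the disputed word.** Inputs: 83 deaths, HR 0.65, one-sided 0.15 (Sections 16.13 and 16.15).

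Power = Φ(√83/2 × |ln 0.65| − z₀.₈₅) = Φ(4.555 × 0.431 − 1.036) = Φ(0.926) = 82.3% without the interim look. Applying the futility look at 42 deaths (p > 0.529) gives 80.3%, against the stated 80% and the table's 79.4%. At HR 1 the chance of success is 14.1%, as in the table. Power follows from the death count. Accrual also agrees: 106 + 14 = 120.

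**2. Which passage governs the OS set?**

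| Section | Purpose | Removes treated major violations from analysis? |
|---|---|---|
| 16.13 | analysis rule for OS | No |
| 16.54 | analysis rule for adverse events | No |
| 13.5 | follow-up and data submission | No; raises a doubt and keeps survival follow-up |
| 16.2 | accrual allowance | No; contains no replacement rule |

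Only Section 16.13 states who enters the OS analysis. The follow-up in Section 13.5 supplies the deaths it needs. Both sections that define a set keep these patients.

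**3. Size for ORR.** The documents give no expected number of violations. As a ceiling, assume that all 14 extra patients are treated major violations, 7 per arm, with no responders. The denominator is then 53 or 60.

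| Responders | Out of 60 (95% Clopper-Pearson) | Out of 53 (95% Clopper-Pearson) | Shift |
|---|---|---|---|
| 10 | 16.7% (8.3 to 28.5) | 18.9% (9.4 to 32.0) | 2.2 points |
| 20 | 33.3% (21.7 to 46.7) | 37.7% (24.8 to 52.1) | 4.4 points |

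The intervals on 53 are 22.6 and 27.3 points wide. If both arms lose the same number, both rates move together. With 12 responders per arm and a 5-versus-2 split of exclusions, the rates are 12/55 = 21.8% and 12/58 = 20.7%, a gap of 1.1 points. Placing all 14 in one arm gives 12/46 = 26.1% against 12/60 = 20.0%, but nothing in the plan suggests such a split.

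**4. Size for OS if Section 16.13 were ignored.** Simulation with 60 treated patients per arm, uniform accrual over 15 months, exponential survival, control median 6.5 months, unstratified log-rank test and no interim look. Violations are unrelated to prognosis. The data cut is at the 83rd death among non-violators. The table shows how often the two sets give different go/no-go results.

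| Violations in total | HR 1 | HR 0.80 | HR 0.65 |
|---|---|---|---|
| 2 | 2.1% | 4.0% | 2.6% |
| 7 | 4.5% | 7.8% | 5.1% |
| 14 | 6.5% | 11.3% | 7.4% |

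This is disagreement, not error: at HR 1 with 7 per arm excluded, success was 14.9% under either set.

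Error moves only if the excluded patients are both prognostically unusual and unevenly labelled. With 5 control and 2 panitumumab exclusions of patients at half the hazard, one-sided error goes from 14.8% to 19.0%. A 3-versus-3 split leaves it unchanged (15.8% against 15.6%), and 2-versus-1 moves it by about one point. With the 5-versus-2 split and doubled hazard, power goes from 83.1% to 77.6%. Part of that gap arises because the common cut gives the larger set more deaths (about 89 against 83). With each set cut at its own 83rd death, power is 81.3% against 78.1%.

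**The case for a change.** The best case for a change runs as follows. Section 16.13 limits its definition to OS, so strictly nothing assigns a set to ORR or CBR. Section 13.5 names the same primary end point and doubts it. Section 16.2 lists major treatment violation separately from ineligibility and cancellation, which makes sense only if such patients are expected not to count. The timeline fits that reading: the 83rd death is expected at about month 25 if 106 patients count and month 22 if all 120 do, and Section 16.3 says about 25. With known treatment and no named decider, the choice could follow the outcomes.

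Part of this stands. ORR and CBR lack a definition, and the allowance in Section 16.2 sits awkwardly with Section 16.13.

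The rest does not carry the conclusion. The month-25 projection shows that the designers planned on 106 contributing patients; it cannot show which losses made up the 14, and ineligible and never-treated patients leave the Section 16.13 set anyway. A doubt voiced in a follow-up section does not override an explicit analysis rule, and that rule leaves the analyst no discretion over an eligible, treated patient. Nor is a missing scan certain for violators: Section 18.1 lists RECIST measurements at end of treatment, and a violation may be confirmed only after a restaging.

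**Conclusion.** The concern does not call for a change. OS, the only endpoint behind the go/no-go, has an explicit set that includes treated patients with a major violation, and their survival is followed. The gap for ORR and CBR is one that analysts fill sensibly: use the Section 16.13 set, count patients without a post-baseline assessment as non-responders, and read the 12 months as the window in which a response must occur.

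If someone filled the gap differently, the effect on ORR would be about 2 to 4 points at the assumed ceiling of 7 treated violations per arm, well inside the confidence intervals and with descriptive p-values. The OS shifts require departing from Section 16.13 and also assuming a number, a lopsided split and an altered prognosis that the documents do not support. This conclusion rests on the sponsor applying Section 16.13 as written.

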16.53 Clinical Benefit Rate

Clinical benefit rate is defined as the number of patients with a complete response (CR), partial response (PR), or stable disease for ≥ 6 months (as defined by the RECIST 1.1) divided by the number of evaluable patients in each arm. Confidence intervals for the true success proportion will be calculated according to the approach of Clopper and Pearson.

16.54 Adverse Events

All eligible patients who have initiated treatment will be considered evaluable for adverse event analyses. The maximum grade for each type of adverse event will be recorded for each patient, and frequency tables will be reviewed to determine adverse event patterns. The overall adverse event rates for grade 3 or higher adverse events will be compared using Chi-Square or Fisher's Exact tests.

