8.0 Dosage Modification Based on Adverse Events

Subjects will be monitored continuously for AEs from the date of first dose of study drug and for 30 days after the last dose of study drug. Subjects will be instructed to notify their treating physician of any and all AEs. All AEs should also be managed with supportive care at the earliest signs of toxicity. Subjects should receive appropriate supportive care measures as deemed necessary by the Investigator. Suggested supportive care measures for the management of adverse events are outlined in Section 9.0.

Subjects experiencing one or more AEs due to study drug(s) may require dose modification(s) as described in Sections 8.1, 8.2, and 8.3. If multiple adverse events are seen, administer dose based on greatest reduction required for any single adverse event observed. Reductions or increases apply to treatment given in the preceding cycle and are based on adverse events observed since the prior dose. At the discretion of the Investigator, dose modifications are permitted outside of those provided in the protocol if the Investigator feels it is in the interest of the subject's safety (e.g., due to multiple toxicities, persistent toxicities, intercurrent illness, or short term compliance or monitoring issues, etc.). Subjects may need to be followed at least weekly when the study drug is held for clinically significant toxicity until the toxicity returns to Grade ≤ 1 or is determined to be controlled, chronic, or irreversible.

Dosing interruptions are permitted in the case of medical / surgical events or logistical reasons not related to study therapy (e.g., elective surgery, unrelated medical events, patient vacation, and/or holidays). Subjects should be placed back on study therapy within 4 weeks of the scheduled interruption, unless otherwise discussed with the Lead PI. The reason for interruption should be documented in the patient's study record.

ALERT: ADR reporting may be required for some adverse events (See Section 10)

8.1 Panitumumab: This section applies to adverse events associated with panitumumab. For adverse events associated with regorafenib, please refer to Section 8.2 and for TAS-102, please refer to Section 8.3.

* Located at [REDACTED]

** Use the following to describe actions in the Action column:

- Omit = Treatment is not given for this cycle
- Hold/Delay = Treatment can be made up as part of this cycle
- Discontinue = Treatment is totally stopped

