16.4.2 Adverse Event Monitoring and Stopping Rules

The monitoring rule specified below is based on the knowledge available at study development. We note that the Adverse Event Monitoring Rule may be adjusted in the event of either (1) the study re-opening to accrual after any temporary suspension or (2) at any time during the conduct of the trial and in consideration of newly acquired information regarding the adverse event profile of the treatment(s) under investigation. The study team may also choose to suspend accrual because of unexpected adverse event profiles that have not crossed the specified rule below.

Accrual may be temporarily suspended to this study if at any time we observe events considered at least possibly related to study treatment (i.e., an adverse event with attribute specified as "possible", "probable", or "definite") that satisfy any of the following criteria for **each arm separately**:

- If at any time, 4 of the initial 10 treated patients, or 33% or more of all patients (when accrual is greater than 10 patients) have experienced a grade 4+ adverse event at least possibly related to treatment.

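### Section 16.54 leaves treated patients later ruled ineligible out of the adverse event analysis, although the 16.4.2 stopping rule counts treated patients without that filter

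*Combined protocol and SAP*

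**What the plan says.** Section 16.54 defines the set: "All eligible patients who have initiated treatment will be considered evaluable for adverse event analyses". The comparison made on it is also given there: "The overall adverse event rates for grade 3 or higher adverse events will be compared using Chi-Square or Fisher's Exact tests". No supplementary analysis of all treated patients is specified.

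Section 13.4 makes ineligibility something that can be found late: "A patient is deemed *ineligible* if after registration, it is determined that at the time of registration" a criterion was not met. It has a branch for patients already dosed: "If the patient received treatment, all data up until the point of confirmation of ineligibility must be submitted". Such patients go directly to event monitoring, or off study if applicable. On further treatment it says: "The patient may continue treatment off-protocol at the discretion of the" physician, subject to safety and proper registration. Section 13.5 has a parallel cut-off for major violations: "All data up until the point of confirmation of a major violation must be submitted".

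Section 8.0 sets a different AE window, from first dose "and for 30 days after the last dose of study drug". The stopping rule in 16.4.2 is applied to each arm separately. It counts "4 of the initial 10 treated patients" and then, beyond 10 patients, a 33% threshold among all patients. It does not mention eligibility.

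**The concern.** Safety analysis follows exposure: a patient who took the drug can be harmed by it whether or not an entry criterion was met. Under 16.54 a finding made after treatment has begun decides whether that patient's toxicity is reported. Some criteria concern organ function or medical risk (laboratory limits in 3.19c, cardiac history in 3.29e to 3.29g, interstitial lung disease in 3.29i, hypertension in 3.29k, bleeding in 3.29m). Failing one of these could go together with a different AE rate. The two arms are also visibly different (an intravenous antibody against oral tablets), so omissions need not fall equally.

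At stake is goal 2.24, the comparison of safety and tolerability. A related Grade 4 or higher event in a treated but ineligible patient could count towards suspending accrual under 16.4.2 and yet be missing from the final AE tables.

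**Working it through.** **1. The plan's own figure.** Section 16.2 gives 106 eligible patients plus 14 for ineligibility, cancellation, major treatment violation or other reasons. 106 + 14 = 120, the stated maximum accrual. The allowance is 14/120 = 11.7%.

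**2. What the 14 can and cannot tell us.** By 13.6 a cancellation never received treatment, so it does not belong in a safety set. An eligible patient with a major violation is not excluded by 16.54. Only treated and ineligible patients are lost, and their number, k, is not given. On the plan's figures k lies between 0 and 14.

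**3. Effect on one arm's Grade 3+ rate.** Let n be the patients treated in the arm, p the rate in eligible patients and q the rate in omitted patients. Then:

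- reported rate = p
- all-treated rate = [(n − k)p + kq]/n
- understatement = k(q − p)/n

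The documents give neither p nor q. As assumptions, take n = 60 (120/2), p = 30%, q = 30%, 50% or 70%, and all k patients in one arm, which is the unfavourable case.

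| k | share of 120 | q = 30% | q = 50% | q = 70% |
|---|---|---|---|---|
| 2 | 1.7% | 0 | 0.7 points | 1.3 points |
| 4 | 3.3% | 0 | 1.3 points | 2.7 points |
| 7 | 5.8% | 0 | 2.3 points | 4.7 points |
| 14 | 11.7% | 0 | 4.7 points | 9.3 points |

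Example: k = 4, q = 50% gives 4 × 0.20/60 = 1.3 points. If q were below p the sign would reverse: q = 10% gives 4 × (−0.20)/60 = −1.3 points, an overstatement. An even split between arms halves each entry. If p and q are the same in both arms, an even split also leaves the difference between arms unchanged.

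**4. Populations side by side.** 16.54: eligible and started treatment. 16.4.2: treated patients, then all patients, with no eligibility condition. The two also differ in grade and attribution, so their counts would not match in any case. The eligibility filter is the part with no stated reason.

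**5. Collection windows side by side.**

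- 13.4 and 13.5: data required up to confirmation, then event monitoring under Section 18.
- 8.0: AEs to 30 days after the last dose of study drug.
- Section 10: serious AEs to the safety visit or 30 days after the last dose of protocol-specified therapy, whichever is later. Later serious events that are at least possibly related stay reportable (10.4, footnote 1), and deaths are covered in 10.311 and 10.533.
- 10.54 and Section 18: late AEs are reportable in survival follow-up, on a form submitted only if applicable.

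The scheduled AE assessments in Section 4.0 belong to active monitoring, which these patients leave. If confirmation coincides with the last protocol dose, scheduled collection of non-serious AEs could fall short of the 8.0 window by up to 30 days.

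**The case against.** Few patients should be affected. Eligibility is verified before registration (6.14), waivers are barred (3.0), and 13.4 judges status as of registration, which limits rulings driven by toxicity. Secondary p-values are descriptive (16.5). The stopping rule already counts treated patients, so monitoring during the trial is not weakened. All of this stands and keeps the point modest, but none of it is a reason to leave dosed patients out of the AE tables.

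Four stronger readings are tempting, and the documents do not support them.

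- A reader might infer that AE collection stops when ineligibility is confirmed. Late-AE, serious-AE and death reporting continue, with no eligibility filter.
- A reader might infer that 13.4 flatly contradicts 8.0. Section 13.4 says what data must be submitted, not that monitoring ends, and treatment after confirmation is off-protocol. The sections are unreconciled rather than plainly opposed.
- A reader might infer that major violations are dropped from the AE analysis. Section 16.54 excludes only ineligible patients; for eligible patients with a major violation the sole issue is the collection window.
- A reader might infer that AE rates are biased downward. Many criteria are molecular, historical or timing items (3.11, 3.14, 3.16, 3.17, 3.23, 3.24), and the plan does not say which are likely to fail.

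**Conclusion.** The point holds for the analysis population. As written, 16.54 removes exposed patients from the comparison that serves goal 2.24 and uses a different basis from 16.4.2. The number removed is not stated; 14 of 120 (11.7%) is a planning ceiling and not an estimate. The direction of bias is not determined by the documents. With an assumed 30% rate in eligible patients and all omissions in one arm of 60, the understatement is 0.7 to 4.7 points if omitted patients have a 50% rate. It reaches 9.3 points at the extreme (k = 14, 70% rate) and is zero if the rates are equal. The collection windows are a secondary matter of reconciliation. The overall survival design, its 83 events and its sample size are not touched.

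**What to change.** Replace the population sentence in 16.54 with: *All patients who received at least one dose of study treatment, regardless of eligibility, are included in AE analyses, grouped by treatment received.* This matches the treated-patient basis of 16.4.2, which then needs no change on this point.

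Reconcile 13.4 and 13.5 with Sections 8.0, 10 and 18, stating that AE data for every treated patient, including those ruled ineligible or in major violation, are collected to 30 days after the last protocol dose. The request stops there: following AEs through off-protocol treatment would be open-ended, since the plan sets no limit on its duration.

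The cost is a wording change in three sections and a small amount of extra AE data entry for a few patients.
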